6 prompt the patient when they ‘break a movement rule’ that has been programmed for them by
7 the clinician. Individualised movement ‘prompts’ may be time-based, such as reducing long
8 periods of sitting without getting up and moving, or may be kinematically-based, such as
9 reducing sitting in an excessively upright position.

10
11 There is no provision for trial-funded ancillary or post-trial care.

12 13 **Clinician recruitment and training**

14 Depending on recruitment and training success, approximately 16 physiotherapists (8 in each
15 city) will deliver the interventions at private physiotherapy clinics. Each physiotherapist will
16 deliver only one CFT treatment arm, to prevent learning (contamination) from experience
17 using the movement sensor output being applied to the CFT-only patients. Physiotherapists
18 will be randomised into either the CFT-only group or CFT-plus-movement-sensor-
19 biofeedback group. Up to four additional physiotherapists will be recruited and trained in
20 each city to act as reserves if required. For physiotherapists to be considered for inclusion in
21 the training program, they will need to have: at least 2 years clinical experience post-
22 graduation; experience treating people with chronic LBP; an interest in applying
23 biopsychosocial management principles via CFT; a willingness to use movement sensors
24 clinically; less than 4 days of prior exposure to CFT training; and a willingness to be

1
2
3 1 observed and videoed for mentoring and feedback purposes while treating a *non-trial* patient
4
5 2 with disabling LBP.
6
7
8 3

9
10 4 The clinician training for both the CFT-only group and CFT-plus-movement-sensor-
11
12 5 biofeedback group will consist of three components: (i) clinical workshops including live
13
14 6 patient demonstrations and mentoring of the physiotherapists while treating patients, (ii)
15
16 7 online resources (e.g. e-book and training videos) and (iii) Facebook private support group
17
18 8 pages.
19
20
21 9

22 23 24 10 *CFT training*

25
26 11 Six clinical workshops will be conducted (a two-day workshop every month for 6 months) in
27
28 12 each city where both CFT-only and CFT-plus-movement-sensor-biofeedback groups will
29
30 13 train together. A final single day workshop will be held for each group separately when
31
32 14 clinicians will need to demonstrate a pre-defined level of competency, as evaluated by the
33

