- 2 • Pain catastrophisation (Pain Catastrophizing Scale)³³
- 3 • Pain self-efficacy (Pain Self-efficacy Questionnaire)³⁴
- 4 • Fear of movement (physical activity subscale of the Fear Avoidance Beliefs Questionnaire)³⁵
- 6 • Patient-perceived global improvement (1 question)³⁶
- 7 • Patient satisfaction with care and treatment (1 question)³⁷
- 8 • Adverse events (defined as any morbidity or events causing unwarranted distress to a participant that were potentially related to any trial-related intervention). Clinicians and follow-up questionnaires will inquire about any adverse events.
- 11 • Lumbosacral movement will be measured in both CFT treatment groups using ViMove2 wearable wireless sensors and used in the mediation analysis.
- 13 • Direct health costs attributable to consumption of health care resources (measured using extracts from Medicare and Pharmaceutical Benefits databases and direct patient reports) and productivity costs (measured using the iMTA Productivity Cost Questionnaire³⁸).

17 **Sample size calculation**

18 The sample size was calculated for the primary outcome using the program STATA. A total
19 of 492 patients (164 per group) will be recruited to detect a difference of 2 points (0-24 scale)
20 on the RMDQ between the CFT-only group and CFT-plus-movement-sensor-biofeedback
21 group, $p < 0.05$, 80% power, a common standard deviation of 6 points and a worst-case
22 scenario of 20% drop-out rate. Based on our pilot study results^{20 39}, we hypothesise that the
23 CFT-plus-movement-sensor-biofeedback group would have an average score of 7.5 points on
24 the RMDQ and the Usual care group would have a score of 11.5 points. Pragmatically and
25 arbitrarily, we assume the CFT-only group will have a mean outcome that is half-way (9.5)

1 between the other two groups and so we will power the trial to detect this as the smallest
2 likely between-group difference ($11.5-9.5=2.0$).

4 **Blinding**

5 Patients will not be informed of any anticipated results of the trial and will be told that the
6 trial is comparing usual care to two evidence-based interventions. All outcome measures will
7 be either self-reported by patients via web-based questionnaires or collected via the
8 movement sensors or MBS/PBS registers. Unblinded clinicians will deliver only type of one
9 treatment and play no role in collecting data, other than performing a standardised movement

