10 protocol with the resultant movement data being automatically uploaded by the sensors to a
11 server without clinician input. Statisticians will be blind to groups.

13 **Statistical analysis**

14 Almost all participant-reported data will be entered directly into an electronic database,
15 where range values are automatically checked. In addition, all data will be checked for range
16 values and outliers prior to analysis.

18 *Treatment efficacy analysis*

19 Repeated-measure linear mixed models will be used to assess the effect of treatment on pain-
20 related physical activity limitation across all time points (3, 6, 13, 26, 40 and 52 weeks), with
21 the primary comparison being a formal test of adjusted mean differences between groups at
22 13 weeks using intention-to-treat principles. Appropriate sensitivity analyses will be
23 performed on multiple imputed datasets. Estimates of treatment effect will be adjusted for
24 baseline scores of symptom duration, pain intensity, activity limitation (RMDQ score),
25 treatment expectations and significant clinician cluster effects.

1
2
3 1 The secondary outcome measures will be evaluated using the equivalent repeated-measure
4
5 2 linear mixed models.
6
7
8 3

9
10 4 As widely recommended, we will focus on reporting the size of the effect and its uncertainty
11
12 5 (including describing compatibility intervals and p-values) rather than making judgements
13
14 6 based on an arbitrary p-value threshold⁴⁰⁻⁴². In the papers that report the outcomes of this
15
16 7 clinical trial, effect sizes will be discussed relative to those obtained by other interventions in
17
18 8 comparable populations.
19
20
21 9

22 23 24 10 *Analysis of economic efficiency*

25
26 11 Direct healthcare and indirect (productivity) costs incurred by participants will be measured
27
28 12 over the 12-month follow-up period. Direct health costs will be collected using Medicare
29
30 13 Benefits Scheme (MBS) and Pharmaceutical Benefits Scheme (PBS) database extractions,
31
32 14 and patient questionnaires to capture other health care costs (e.g. hospitalisations). Indirect
33
34 15 health costs (e.g. travel to appointments) and productivity costs (including absenteeism and
35
36 16 presenteeism) will also be captured in the 3-monthly patient questionnaires. Productivity
37
38 17 costs will be measured using the 'iMTA Productivity Cost Questionnaire'. Productivity costs
39

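### Clinician clustering is adjusted for only if significant; if therapists differ, this pre-test can drop a real variance component and leave intervals too narrow, mainly for CFT-only versus CFT-plus-biofeedback

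*Supplement*

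**What the plan says.** All references are to the revised protocol (R1); no separate analysis plan is shown.

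- **Treatment efficacy analysis.** The primary analysis is a repeated-measures linear mixed model of the RMDQ, with "the primary comparison being a formal test of adjusted mean differences between groups at" 13 weeks. The adjustment list ends with "treatment expectations and significant clinician cluster effects". No test, threshold, ICC or random-effect structure is named. Secondary outcomes use equivalent models. The section also says that reporting will stress effect sizes and compatibility intervals over a p-value threshold.
- **Clinician recruitment and training.** "Depending on recruitment and training success, approximately 16 physiotherapists (8 in each" city) will deliver the interventions. They are randomised between the two CFT arms, and each will "deliver only one CFT treatment arm, to prevent learning (contamination) from experience" with the sensor output. Up to four reserves per city may be added.
- **Sample size calculation.** It assumes a 2-point difference, "80% power, a common standard deviation of 6 points and a worst-case" "scenario of 20% drop-out rate", with 164 per group. Clustering and a design effect are not mentioned.
- **Moderation analysis.** The interaction terms are assessed in the same mixed models.

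**The concern.** Because each therapist works in one CFT arm only, a difference between the arms is partly a difference between two small sets of therapists. That variance belongs in the standard error whether or not it reaches significance. A test on about 16 therapists can easily miss an ICC that still matters. When it does, the model treats all patients as independent and reports an interval that is too short. The stress on intervals does not help, since they rest on the same standard error.

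The comparison most exposed is CFT-only versus CFT-plus-biofeedback. The protocol lists measuring the added contribution of the sensors as a strength, and it is the comparison named in the sample size paragraph. Comparisons with usual care are exposed on one side only, because usual care has no trial therapist.

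**Working it through.** **Inputs from the protocol.** 164 per group; difference 2; SD 6; alpha 0.05 (two-sided taken); 20% drop-out; about 16 therapists, plus up to 8 reserves.

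**Assumptions.** Equal split, so 8 therapists per CFT arm; ICC from 0 to 0.10; pre-test at 5%; one time point; balanced caseloads.

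**The plan's own figure.** n = 2 × (1.96 + 0.842)² × 6² / 2² = 141.3, so 142 per arm. With drop-out, 142 / 0.8 = 177.5, so 178. The stated 164 is not reproduced. That is a separate matter and does not affect what follows. With 164 recruited, 164 × 0.8 = 131 remain per arm, and 131 / 8 = 16.4, or about 16 patients per therapist. Power with 131 per arm and no clustering is 77%.

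**Step 1: what is lost when therapist is dropped.** The design effect is 1 + (m − 1) × ICC with m = 16. At ICC 0.02 it is 1 + 15 × 0.02 = 1.30, so the true standard error is √1.30 = 1.14 times the one reported.

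**Step 2: power of the pre-test.** F = between-therapist mean square / within-therapist mean square. The degrees of freedom are 2 × 8 − 2 = 14 and 16 × 15 = 240, and the 5% critical value is 1.73. For a given ICC, F follows [1 + 16 × ICC / (1 − ICC)] times a central F(14, 240). At ICC 0.02 the multiplier is 1.33, which gives power of 20%.

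**Step 3: the two-stage rule with no true effect.** If F is significant, arms are compared on therapist means; otherwise an ordinary patient-level t test is used. There were 200,000 simulated trials per ICC.

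| ICC | Design effect | Pre-test power | Error when dropped, CFT v CFT | Overall error, CFT v CFT | Overall error, CFT v usual care |
|---|---|---|---|---|---|
| 0 | 1.00 | 5% | 5.0% | 4.8% | 4.9% |
| 0.01 | 1.15 | 11% | 6.7% | 6.0% | 5.5% |
| 0.02 | 1.30 | 20% | 8.7% | 7.1% | 5.8% |
| 0.03 | 1.45 | 31% | 10.4% | 7.6% | 6.1% |
| 0.05 | 1.75 | 51% | 14.3% | 7.9% | 6.2% |
| 0.10 | 2.50 | 84% | 22.7% | 6.5% | 5.7% |

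The overall error mixes the dropped and kept cases. At ICC 0.05, where the error is about 2% when the term is kept, 0.51 × 2% + 0.49 × 14.3% ≈ 8%. Always keeping the therapist term gives about 5% at every ICC.

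**Sensitivity (ICC 0.01 to 0.10, CFT v CFT).** With 20 patients per therapist the overall error is 6.0% to 7.9%. With all reserves used (12 therapists per arm, 11 patients each) it is 5.7% to 7.2%.

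**Step 4: power if therapist is always modelled.** SE = 6 × √(2 × design effect / 131), with m = 16.4, and a t test on 14 degrees of freedom (critical value 2.145).

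| ICC | Design effect | SE | 2 / SE | Power |
|---|---|---|---|---|
| 0 | 1.00 | 0.74 | 2.70 | 71% |
| 0.01 | 1.15 | 0.80 | 2.51 | 65% |
| 0.03 | 1.46 | 0.90 | 2.23 | 55% |
| 0.05 | 1.77 | 0.99 | 2.03 | 47% |

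**The case against.** Several points on the other side stand.

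- **The harm is conditional.** A reader might infer that the standard errors are too small and that type I error exceeds 5%, full stop. The documents do not support that. They give no ICC, there is no inflation at ICC 0, and the standard error is understated only in analyses where the term is dropped. Shared workshops, a competency check and video fidelity review may also keep therapists alike, though they do not show that the ICC is zero.
- **The pre-test is not always weak.** Little power is a fair description up to an ICC of about 0.03. Power is about half at 0.05 and 84% at 0.10.
- **Usual-care comparisons are only slightly affected.** They make up two of the three pairwise comparisons.
- **The simulation is a stand-in.** The 5% F test is an assumption, and a looser level would shrink the inflation. The planned model is baseline-adjusted with repeated measures.
- **Some of the remedy is analysis-plan detail.** The degrees-of-freedom method and the covariance structure are commonly left to a separate plan, so their absence is not the fault here. The stated significance condition is.

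Two defences do not remove the problem. Statisticians blind to group are less able to steer the model choice, but the pre-test's error rate is the same. If significant was meant as substantial, no threshold is given, and the model would still depend on the outcome data.

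**Conclusion.** The point holds in conditional form. As worded, the rule can drop a variance component that the design builds into the CFT-only versus CFT-plus-biofeedback comparison. If therapists differ at all, error for that comparison rises moderately, to about 6% to 8% for ICC 0.01 to 0.05. That corresponds to interval coverage of about 92% to 94% in place of 95%. The departure against usual care is minor.

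The larger error rates in the dropped-term column apply only to trials where the pre-test fails. They should not be read as the error of the plan as a whole. All sizes rest on the assumed ICC, the 5% pre-test, one time point and balanced therapists.

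**What to change.** Delete the word significant from the adjustment sentence. State that a therapist random effect is always fitted for participants in the two CFT arms, with usual-care participants unclustered, whatever its estimate or p-value. Name a small-sample method for the degrees of freedom, such as Kenward-Roger or Satterthwaite; this can sit in the analysis plan. Carry the same structure into the secondary-outcome and moderation models, which reuse this one. Settle the wording before unblinding.

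The change needs no extra patients, visits or data. Its price is wider intervals and lower honest power between the CFT arms, as shown in Step 4, against the 77% obtained when therapist is ignored. The protocol should disclose that loss. It is not a reason to keep the pre-test, because power figures that ignore therapist are overstated whenever therapists differ.

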41 be provided for both clinician groups separately to provide a forum for the discussion of
42
43 challenges faced when implementing the intervention or with technical issues related to the
44
45 sensors. The trainers will contribute to the Facebook discussion and 3-monthly meetings.
46
47
48
49
50

51 *Treatment fidelity checking*

52
53 Every seventh participant of each clinician will be selected, and their treatment monitored by
54
55 the appropriate clinician trainer to ensure ongoing treatment fidelity. If the seventh
56
57 participant does not consent to this occurring, each subsequent participant of that clinician
58
59
60

1 will be asked until one consents. This process is recommended in the Spillane (2007)²⁷
2 framework for implementation fidelity in trials. This will take the form of video recordings of
3 three consultations (a consultation early in the treatment process, one in the middle and one
4 close to the end of the treatment period) that will be reviewed by a randomly selected
5 clinician trainer (POS, JPC or KOS) with brief feedback provided if required.

7 **Data collection and outcome measures**

8 Data collection will occur at baseline, and at 3, 6, 13, 26, 40 and 52 weeks. Where ever
9 possible, all data will be completed on-line directly into the trial database. Alternatively,
10 patients can complete follow ups over the telephone with a researcher. If participants do not
11 complete follow-ups within 2 day of the scheduled date, they will receive an email reminder
12 and then 2 days later will be contacted by one of the study team. Data collected via the ViMove
13 sensors at each clinical visit will be directly uploaded to a database. A detailed description of
14 the data collected at each time point is presented in Table 1.

16 *Primary outcomes*

17 The primary clinical outcome will be pain-related physical activity limitation measured using
18 the Roland Morris Disability Questionnaire^{28 29} (RMDQ). For the economic efficiency (cost-
19 utility) analysis, the primary outcome of clinical effect will be quality-adjusted life years
20 calculated using the area under the curve approach based on responses to the EQ-5D-5L
21 questionnaire³⁰ across each of the assessment time points.

23 *Secondary outcomes*

24 The secondary outcomes include:

- 25 • Pain intensity (three numeric rating scales)³¹

- 1 • Patient-specific activity limitation (Patient-Specific Functional Scale)³²

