40 18 measured at specific time points will be extrapolated to the full one-year period using an area
41
42 19 under the curve approach. All costs will be calculated using a 2019-2020 financial base year.
43
44 20 Hospital costs will be valued using the National Weighted Activity Unit calculators for the
45
46 21 2019-2020 year.
47
48
49
50
51 22

52
53 23 An incremental cost-utility analysis will calculate the difference in costs between intervention
54
55 24 and control groups divided by the difference in quality-adjusted life years. Incremental cost-
56
57 25 utility analyses will be undertaken from societal (primary analysis) and health service
58
59
60

1 (secondary analysis) perspectives. There will also be analyses undertaken for valuation of
2 productivity costs using human capital (primary analysis) and friction (secondary analysis)
3 methods. Bootstrap resampling (2000 replications of original sample size) will be used to
4 generate a 95% confidence ellipse surrounding the incremental cost-utility estimate. Cost-
5 effectiveness acceptability curve analyses will be undertaken if the intervention is not found
6 to dominate the control condition.

7 8 Moderation analysis

9 To investigate if treatment effect is moderated by cognitive flexibility, baseline activity
10 limitation, baseline pain, catastrophisation or self-efficacy (all groups), the interaction term
11 between the potential moderator and the treatment group variable will be assessed in the
12 repeated-measure linear mixed models for pain-related activity limitation and pain intensity
13 described above. Only in the CFT groups, similar moderation analysis will also occur using
14 the STaRT MSK Tool^{43 44} (measured at baseline), therapeutic alliance⁴⁵ (measured at 3
15 weeks) and participant-rated adherence to the treatment program measured at weeks 3, 6 and
16 12 with a study-specific single question ('How would you rate your adherence to the
17 treatment program your physiotherapist has recommended?' 0-10 no adherence to complete
18 adherence).

19 20 Mediation analysis

21 To investigate whether improvement in patients' activity limitation was mediated by
22 correction of habituated functional movement behaviors, or changing patient's pain-related
23 cognitions and emotions, a multilevel structural equation model framework will be utilised.
24 Investigation of the mediation roles of cognitions and emotions will occur using data from all

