
Version 1, 12 April 2019

Table 1: Trial data collected and their purpose

Construct	Measure	Time points (weeks)	Purpose
Age	Date of birth	0	Describe population
Sex	Male/Female	0	Describe population
Duration of episode	Weeks	0	Describe population
Duration since care-seeking	Weeks	0	Describe population
Previous lifetime episodes	Number	0	Describe population
Height	Centimeters	0	Describe population
Weight	Kilograms	0	Describe population
Education	Categorical	0	Describe population
Current role	Categorical	0	Describe population
Employed	Yes/No	0	Describe population and analysis of economic efficiency
Occupation	Open text	0	Describe population and analysis of economic efficiency
Hours working	Hours	0	Describe population and analysis of economic efficiency
Days working	Days	0	Describe population and analysis of economic efficiency
Sick leave last 3/12	Yes/No	0, 12, 26, 40 and 52	Describe population and analysis of economic efficiency
Days of sick leave 3/12	Days	0, 12, 26, 40 and 52	Describe population and analysis of economic efficiency
Pain-related physical activity limitation	Roland Morris Disability Questionnaire ⁴⁷	0, 3, 6, 12, 26, 40 and 52	Describe population, primary outcome, analysis of economic efficiency

Functional limitation	Patient-Specific Functional Scale ⁴⁸	0, 3, 6, 12, 26, 40 and 52	Secondary outcome
Pain intensity	Numeric Pain Rating Scales ³¹	0, 3, 6, 12, 26, 40 and 52	Describe population, secondary outcome
Fear avoidance beliefs	Fear Avoidance Beliefs Questionnaire (physical activity sub-scale) ³⁵	0, 12, 26, 40 and 52	Describe population, secondary outcome, mediator
Analgaesic use	Participant self-report text box	0	Describe population, secondary outcome (when matched to 12-month Pharmaceutical Benefits Scheme data)
Catastrophising	Pain Catastrophizing Scale ³³	0, 3, 6, 12, 26, 40 and 52	Describe population, secondary outcome, mediator and moderator
Pain self-efficacy	Pain Self-efficacy Questionnaire ³⁴	0, 3, 6, 13, 26, 40 and 52	Describe population, secondary outcome, mediator and moderator
Quality-adjusted life years	EuroQOL EQ-5D-5L ⁴⁹	0, 12, 26, 40 and 52	Analysis of economic efficiency outcome
Treatment expectations	A tailored question, based on Rofail, Myers and Froggatt 2016 ⁵⁰	0 (post-randomisation)	Clinical effectiveness baseline covariate
Confidence in intervention	A tailored question, based on Rofail, Myers and Froggatt 2016 ⁵⁰	3 (CFT groups only)	Mediator
Cognitive flexibility	Cognitive Flexibility Inventory ⁵¹	0	Moderator

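### The economic analysis specifies no adjustment of the QALY difference for baseline EQ-5D-5L, although week-0 utility is collected and forms part of the QALY area

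*Supplement*

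**What the plan says.** All references are to the revised protocol (July 2019) in the supplement.

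- **Primary outcomes.** The primary outcome of the economic analysis is the QALY, "calculated using the area under the curve approach based on responses to the EQ-5D-5L".
- **Table 1, EQ-5D-5L row.** Time points and purpose read "0, 12, 26, 40 and 52 Analysis of economic efficiency outcome". Week 0 is therefore collected and is assigned to the economic analysis.
- **Analysis of economic efficiency.** "An incremental cost-utility analysis will calculate the difference in costs between intervention" "and control groups divided by the difference in quality-adjusted life years". Uncertainty comes from 2000 bootstrap resamples, shown as a 95% confidence ellipse. The section names no regression model and no covariates.
- **Treatment efficacy analysis.** The protocol's one list of adjustment covariates is here. It opens with "baseline scores of symptom duration, pain intensity, activity limitation (RMDQ score") and adds treatment expectations and clinician clustering. EQ-5D-5L is not on it.
- **Secondary outcomes.** These are to be analysed by mixed models equivalent to the primary one. The list includes health and productivity costs but not QALYs.
- **Productivity costs.** Values "measured at specific time points will be extrapolated to the full one-year period using an area" under the curve. Table 1 schedules the productivity questionnaire (iPCQ) at weeks 12, 26, 40 and 52 only. Days of sick leave over the previous three months are collected at "0, 12, 26, 40 and 52", with the economic analysis as a stated purpose.

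**The concern.** Baseline utility affects an area-under-the-curve QALY in two ways. It is the left-hand end of the first trapezoid, and people who start with higher utility tend to have higher utility later. If the arms differ at baseline by chance, an unadjusted comparison therefore shows part of that difference as QALYs gained or lost. Regression on baseline utility removes that part in expectation under a linear model and narrows the interval.

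The clinical section names baseline covariates, including the baseline value of its own outcome. The economic section does neither for its primary outcome, and because QALYs are not among the secondary outcomes, no stated route brings baseline utility in as a covariate. What is at stake is the precision and the conditional accuracy of the QALY difference, which is the denominator of the cost-utility ratio. The RMDQ comparison at 13 weeks is not affected.

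**Working it through.** The documents give no utility SD, target QALY difference or expected ratio, so there is no figure of the plan's to reproduce.

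**Inputs from the documents:** EQ-5D-5L at weeks 0, 12, 26, 40 and 52; iPCQ at weeks 12, 26, 40 and 52 (Table 1); 164 per arm and a worst case of 20% drop-out (Sample size calculation).

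**Assumed inputs:** utility SD 0.15 to 0.25; slope *b* of follow-up utility on baseline utility 0 to 0.7.

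**Step 1, direct weight of week 0.** By the trapezoidal rule, w0 = (12/2)/52 = 0.115. The other weights are 13/52 = 0.250, 14/52 = 0.269, 13/52 = 0.250 and 6/52 = 0.115.

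**Step 2, pass-through.** A baseline difference *d* moves the unadjusted QALY difference by d × [w0 + (1 − w0) × b]. The bracket is 0.115 at b = 0, 0.381 at b = 0.3, 0.558 at b = 0.5 and 0.735 at b = 0.7.

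**Step 3, chance imbalance.** SE = SD × √(2/164) = 0.0166, 0.0221 and 0.0276 for SDs of 0.15, 0.20 and 0.25. Multiplying by 1.96 gives 0.0325, 0.0433 and 0.0541.

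**Step 4, 95% extent in the QALY difference** (step 3 × step 2):

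| Assumed SD | b = 0 | b = 0.3 | b = 0.5 | b = 0.7 |
|---|---|---|---|---|
| 0.15 | ±0.0037 | ±0.0124 | ±0.0181 | ±0.0239 |
| 0.20 | ±0.0050 | ±0.0165 | ±0.0241 | ±0.0318 |
| 0.25 | ±0.0062 | ±0.0206 | ±0.0302 | ±0.0398 |

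**Step 5, sensitivity of the middle case** (SD 0.20, b = 0.5, ±0.024).
- If the 12-week point is week 13, as in the text, w0 = 6.5/52 = 0.125 and the bracket is 0.125 + 0.875 × 0.5 = 0.563, giving ±0.024.
- If EQ-5D-5L were collected at every assessment, w0 = 1.5/52 = 0.029 and the bracket is 0.029 + 0.971 × 0.5 = 0.514, giving ±0.022.
- With 131 per arm (164 × 0.80), it is ±0.027.

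When b is well above zero, most of the effect comes through the correlation with later utility, so the exact schedule matters little.

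**Step 6, precision.** Adjusting for a covariate that correlates r with the outcome cuts the variance by r². For assumed r of 0.3 and 0.6 the cuts are 0.3² = 9% and 0.6² = 36%.

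**Step 7, productivity area.** From week 12 to week 52 the trapezoids span 52 − 12 = 40 weeks, or 40/52 = 77%. The first 12 weeks (12/52 = 23%) have no left-hand point and no stated rule. If each value stands for the interval before it, coverage is 12 + 14 + 14 + 12 = 52 weeks.

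**The case against.** **Silence is not a method.** The quoted sentence defines a ratio, and the definition is the same whether its two differences are adjusted or not. A reader might infer that the plan commits to raw differences; it does not say so. No separate health-economic plan is shown, and covariates are often left to one. That stands against any claim of error. It does not remove the case for an improvement: the section already fixes the perspective, the productivity valuation method, the base year and the bootstrap count, and for further analysis-plan details the reporting checklist (item 20a) points only to a page of the protocol itself.

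**Week-0 EQ-5D-5L is used.** A reader might infer that it is collected and then ignored. It enters the QALY area with a weight of 0.115. What is unstated is its use as a covariate.

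**Randomisation makes the unadjusted difference unbiased.** This is correct, and resampling participants carries the chance imbalance into the ellipse as ordinary noise. The remaining cost is a wider ellipse, centred off target by whatever imbalance occurred. Allocation cannot be relied on to prevent this, because the Randomisation section names no balancing factors.

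**Costs may already be adjusted.** They are listed as secondary outcomes, which receive models equivalent to the baseline-adjusted primary one. The protocol does not explain how those models relate to the cost-utility ratio, so this stays open for costs. It does not reach QALYs.

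**The missing week-0 iPCQ value does not itself pass imbalance into the result.** A reader might infer that it does, but a value absent from the area cannot enter it directly. A week-0 value would describe losses before randomisation, and the three-month sick-leave item at week 12 covers much of the absence in weeks 0 to 12. What is left is an unstated rule for the first interval.

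**Conclusion.** The point holds as an improvement to an underspecified analysis, not as an error of method. The protocol specifies no baseline-utility adjustment for its primary economic outcome, although the covariate is collected. The chance-imbalance component of the QALY difference has a 95% extent of about ±0.004 (SD 0.15, b = 0) to ±0.040 (SD 0.25, b = 0.7), with about ±0.024 in the middle case. The direct weight of 11.5% follows from Table 1; every SD, slope and correlation is an assumption.

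A reader might express these amounts as a share of the true QALY gain, or call them bias. The documents support neither: they state no expected gain, so any percentage would depend on an invented denominator, and under randomisation the imbalance averages to zero.

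The productivity-cost rule for weeks 0 to 12 is a minor, separate gap.

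**What to change.** In Analysis of economic efficiency, state the following:

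1. The QALY difference is estimated by regression on arm with baseline EQ-5D-5L utility as a covariate, and this regression is repeated within each of the 2000 bootstrap replicates, so that the ellipse and any acceptability curve rest on the adjusted difference.
2. Productivity costs are adjusted for week-0 sick-leave days in the same replicates. Baseline iPCQ cost cannot be used because it is not collected; sick-leave days are the nearest available proxy.
3. Each iPCQ value represents the interval before it, so that the four values cover all 52 weeks and no week-0 value is needed.

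The unadjusted differences can be reported alongside. Fixing this before the data are examined also prevents the choice to adjust from following the observed imbalance. The cost is a few sentences in the plan and a few lines of code; there is no new data collection and no added burden on participants.
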